6.1. Discontinuation of treatment

The investigators and the sponsor can at any time decide that a participant should not have the second infusion due to, for example, adverse events. A participant will be automatically disqualified from receiving the second infusion if any one of the following criteria is met:

1. Decision of investigator or sponsor
2. Request from participant
3. Withdrawal of the participant from the trial
4. Initiation of bone-protective therapy (other than the assigned investigational product)
5. Severe renal impairment (estimated glomerular filtration rate of <35 ml per minute per 1.73 m² of body surface area) at Follow-Up Visit 1
6. Hypocalcemia (serum calcium <2.2 mmol/L) at Follow-Up Visit 1, unless this can be resolved within the time window of the second infusion, i.e., 24 months ± 4 weeks (see Section 9)

A participant's follow-up will continue even if treatment is discontinued, unless the participant wishes to withdraw from the study.

6.2. Concomitant medications

The use of the prescribed vitamin D and of bone-protective medications during follow-up (other than the assigned investigational product) will be reported. The use other concomitant medications during the trial will not be reported, because this is a late-phase trial and no adverse drug interactions are known to exist.¹⁷

Study Name: The Fragility Fracture Trial
Version No: 2
Date: 2020-10-04
EudraCT No: 2019-004766-17

7. Outcomes

7.1. Primary outcome

Due to the high clinical relevance of most fractures, the primary outcome will be time to first new clinical fracture (ICD-10-SE codes: S12-S52, S72, S82, M48.5, M49.5, M80.0A, M80.0J, and M80.0K). Clinical fracture will be defined as any fracture that comes to medical attention, excluding fractures of the facial bones, skull, hands, and feet (ICD-10-SE codes: S02, S62, and S92), which are not generally considered osteoporotic.¹⁰ For the same reason, pathological fractures (e.g., due to cancer or osteomyelitis) will be excluded. High-energy fractures will be included because these are also associated with low bone mineral density.^{11,43}

Participants will be asked about fractures at study contacts, which will take place every 6 months of follow-up (see Section 9). Participants will also have the possibility of reporting fractures to their study center between the scheduled contacts. Participants who withdraw will be asked if they wish to answer questions about incident fractures before they formally withdraw. The Swedish Fracture Register will also be used to trace fractures for patients who consent to registry follow-up.

Fractures identified through interview will be verified through review of medical records by the study site investigator, given that the participant consents to it. Due to limited resources, the sponsor/coordinating investigator will not adjudicate fractures or other outcomes. To reduce the amount of missing data in the 10-year post-study analysis, fractures will be traced centrally by the sponsor using the above-mentioned ICD-10-SE codes in the Swedish National Patient Register. This register records all diagnoses made in inpatient care in Sweden since 1987 and all outpatient secondary (i.e., non-primary) care since 2001.⁴⁴

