7.2. Secondary outcomes

The secondary outcomes are as follows:

1. Time to first non-vertebral fracture (ICD-10-SE: S22.2, S22.3, S22.4-S22.8, S32.1-S32.5, S42, S52, S72, S82)
2. Time to first new non-hip, non-vertebral fracture (ICD-10-SE: S22.2-S22.8, S32.1-S32.5, S42, S52, S72.3-S72.4, S82)
3. Time to first hip fracture (S72.0-S72.2)
4. Time to first new forearm fracture (S52)
5. Time to first clinical vertebral fracture (S12, S22.0, S22.1, S32.0, M48.5, M49.5, M80.0A, M80.0J, and M80.0K)
6. Time to death

Study Name: The Fragility Fracture Trial
Version No: 2
Date: 2020-10-04
EudraCT No: 2019-004766-17

7. Time to first new cardiovascular event (stroke or myocardial infarction) (ICD-10-SE: I21, I60-I64)
8. Time to first new cancer diagnosis (ICD-7-SE: 140-209)
9. Occurrence of fall from standing height or less (ICD-10-SE: W00, W01, W03, W04, W18) not resulting in fracture between baseline and 48 months

Hip fractures are included among non-vertebral fractures and forearm fractures are included among non-hip, non-vertebral fractures. However, hip fractures and forearm fractures will also be assessed separately because these are common and classic types of osteoporotic fractures. Fractures, myocardial infarction, stroke, and cancer events will be identified through self-report and verified by investigators through review of medical records. Participants will also have the possibility of reporting these outcomes to their study center between the scheduled study contacts. Participants who withdraw will be asked if they wish to answer questions about these outcomes before they formally withdraw.

In the 10-year follow-up, myocardial infarction and stroke will be traced using the above-mentioned ICD-10-SE codes in the National Patient Register, SWEDEHEART, and the Swedish Stroke Register. SWEDEHEART is a register that covers most patients in Sweden who are hospitalized for acute coronary syndrome, coronary interventions, or valvular interventions.⁴⁵ The Stroke Register is a register of Swedish stroke patients, although it does not have complete coverage of the population.⁴⁶ At the 10-year follow-up, cancer events will be identified through the Swedish Cancer Register, which records all new cases of cancer in Sweden since 1958.⁴⁷ Deaths will be identified through the Swedish Cause of Death Register and by reports from family members to study centers.⁴⁸

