7.4. Safety outcomes

Based on previous trials of zoledronic acid and the Summary of Product Characteristics of Aclasta,^{17,19-21} the occurrence or worsening of the following pre-specified safety outcomes will be assessed:

1. Post-infusion symptoms
 - a. Influenza-like symptoms
 - b. Pyrexia
 - c. Myalgia
 - d. Headache
 - e. Arthralgia
2. Osteonecrosis of the jaw
3. Osteonecrosis (avascular necrosis) not of the jaw
4. Atypical femur fracture
5. Any atrial fibrillation
6. Serious atrial fibrillation
7. Re-operation of fracture
8. Delayed fracture healing
9. Renal failure
10. Hypocalcemia
11. Ocular event

In the 10-year follow-up, ICD-10-SE codes will be used to trace occurrences of atrial fibrillation (I48), renal failure (N17-N19), hypocalcemia (E835) femur shaft fractures (S722-S724), ocular events (H10-H22), osteonecrosis not of the jaw (M87), and inflammatory conditions of the jaw (K10.2) in Swedish National Patient Register.

8. Safety

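### The primary outcome's code range S12-S52 conflicts with its definition in words, and the component code lists do not fit together; the 10-year tracing and component outcomes are exposed

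*Protocol*

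**What the plan says.** Section 7.1 gives the primary outcome both as codes and in words. The codes are "ICD-10-SE codes: S12-S52, S72, S82, M48.5, M49.5, M80.0A, M80.0J, and M80.0K". The words are "Clinical fracture will be defined as any fracture that comes to medical attention, excluding fractures of the facial bones, skull, hands, and feet", with the exclusions coded as "ICD-10-SE codes: S02, S62, and S92".

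Section 7.2 builds the component outcomes from single categories, some of them split at the fourth character:

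- "Time to first non-vertebral fracture (ICD-10-SE: S22.2, S22.3, S22.4-S22.8, S32.1-S32.5, S42, S52, S72, S82")
- "Time to first new non-hip, non-vertebral fracture (ICD-10-SE: S22.2-S22.8, S32.1-S32.5, S42, S52, S72.3-S72.4, S82")
- "Time to first hip fracture (S72.0-S72.2")
- Clinical vertebral fracture: S12, S22.0, S22.1, S32.0 and the same M codes as the primary outcome.

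Section 7.4 lists the codes for 10-year safety tracing, among them "femur shaft fractures (S722-S724").

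Section 7.1 also describes how events are found. During the trial, participants are asked about fractures and the site checks their reports against medical records, subject to consent. The Swedish Fracture Register is a second source. For the 10-year analysis the sponsor traces fractures in the National Patient Register with the codes already given. Section 12.2 has efficacy outcomes recorded in ICD-10-SE, and Section 13.6 excludes events that neither registries nor medical records can verify.

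**The concern.** Every injury-chapter fracture category that Sections 7.1 and 7.2 name singly ends in 2: S02, S12, S22, S32, S42, S52, S62, S72, S82, S92. A continuous range from S12 to S52 takes in everything between them. Elsewhere the protocol uses a hyphen for a true continuous range (I60-I64 and S22.4-S22.8 in Section 7.2; N17-N19 and H10-H22 in Section 7.4), so a programmer following that convention would select all of S12 to S52.

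Two things are at stake. Where codes alone pick the events, diagnoses that the protocol nowhere lists as fractures would be counted as fractures. If zoledronic acid does not affect those diagnoses, the estimated effect moves toward no difference. And where coded fractures are sorted into component outcomes, a fracture whose code is on no component list counts in the primary outcome and then drops out of the breakdown by site.

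**Working it through.** **1. The plan's own figure.** Inputs from Section 13.10 and Appendix 1: hazard ratio 0.65, 90% power, two-sided 5%, 1:1 allocation, placebo risk 10% over 4 years, dropout 5%.

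- Events: 4 × (1.960 + 1.282)² / (ln 0.65)² = 42.03 / 0.1856 = 226.5, rounded up to 227.
- Risk on zoledronic acid: 1 − 0.90^0.65 = 0.06619.
- Participants: 227 / ((0.10 + 0.06619) / 2) = 2732.
- After dropout: 2732 / 0.95 = 2876, which the plan rounds to 2900.

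The figures reproduce. The S12-S52 range is not an input to them: Section 13.10 gives codes only for the initial fracture (S42, S52, S82) and lists the new fractures by site.

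**2. The range.** Categories from S12 to S52 inclusive: 52 − 12 + 1 = 41. Those in a Section 7.2 fracture list: S12, S22, S32, S42, S52, which is 5. The rest: 41 − 5 = 36, namely S13-S21, S23-S31, S33-S41 and S43-S51 (4 × 9 = 36). None of the 36 appears in a fracture list anywhere in the protocol.

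**3. The components against the primary outcome.** Take S12, S22, S32, S42, S52, S72 and S82 as the intended injury categories, expand each to fourth characters 0 to 9, and compare.

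| Category | Vertebral | Non-vertebral | In neither |
|---|---|---|---|
| S12 | all | none | none |
| S22 | .0, .1 | .2 to .8 | **.9** |
| S32 | .0 | .1 to .5 | **.6 to .9** |
| S42, S52, S82 | none | all | none |
| S72 | none | all | none |

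**4. The split of non-vertebral into hip and non-hip.** The two lists agree on S22, S32, S42, S52 and S82, so only S72 matters.

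| S72 fourth character | Non-vertebral | Hip | Non-hip, non-vertebral |
|---|---|---|---|
| .0 to .2 | yes | yes | no |
| .3, .4 | yes | no | yes |
| **.5 to .9** | yes | **no** | **no** |

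No injury code in a component list lies outside the primary outcome. The mismatch runs one way: some primary events belong to no component.

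**5. S72.2.** Section 7.2 places it in hip fracture (S72.0-S72.2). Section 7.4 places it under femur shaft (S72.2-S72.4). The overlap is not explained.

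**6. Where the codes decide.**

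| Step | What admits an event |
|---|---|
| 4-year, interview | reported fracture, checked against records |
| 4-year, Swedish Fracture Register | entry in a register of fractures |
| 4-year, sorting into components | recorded ICD-10-SE code |
| 10-year, National Patient Register | code alone; no record review is stated |

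The National Patient Register is described in Section 7.1 as holding all inpatient and secondary outpatient diagnoses, so it does not itself restrict the search to fractures.

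**The case against.** The strongest reply is that the range is shorthand. The list jumps from S52 to S72, and the same paragraph excludes S62, so the author is plainly stepping through the categories ending in 2. The sentence also says that the event is a fracture. This stands as evidence of intent and shows which list was meant. It does not make the written range correct in a step that applies the codes.

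A reader might infer that the main 4-year result is miscounted and that the design hazard ratio of 0.65 would be diluted. The documents do not support that. The definition in words requires a fracture, interview reports are checked against records, the other source is a fracture register, and unverifiable events are excluded. Tracing by code alone belongs to the 10-year analysis, which is exploratory objective 8 in Section 3.3. The documents give no frequency for the 36 categories, so any diluted hazard ratio would rest wholly on an assumed rate. Nor do they say what those categories contain; that they are not fracture categories is implied only by the pattern of the listed codes.

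The protocol does not promise that the components partition the primary outcome, and some overlap on purpose, such as forearm within non-hip, non-vertebral. That is fair. But overlap is different from a gap: a non-vertebral fracture that is neither hip nor non-hip is an inconsistency on the outcomes' own names. The protocol does not say which of the unlisted fourth characters are in use, so some gaps may be empty.

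A code may serve both an efficacy list and a safety list, and Section 7.4 prescribes no pooled comparison. That S72.2 would mask an excess of shaft fractures is therefore a possibility, not something shown. The conflicting label remains.

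**Conclusion.** The point holds as a defect in the outcome definitions.

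- **Range.** S12-S52 as written covers 41 categories, 36 of them in no fracture list, and conflicts with the definition in words and with Section 7.2. The consequence falls on the exploratory 10-year tracing. Its direction would be toward no effect if the added diagnoses are unaffected by the drug, which is an assumption; no size can be given from the documents.
- **Components.** S72.5-S72.9, S22.9 and S32.6-S32.9, where in use, leave coded fractures outside the component outcomes. This touches the secondary fracture outcomes at 4 years too, because record review confirms a fracture but nothing says how an unlisted code is then assigned. It does not change the primary count.
- **S72.2.** One code carries two anatomical labels.

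The 4-year primary analysis is not shown to be affected, and the 227 events and 2900 participants stand.

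**What to change.** 1. In Section 7.1, replace S12-S52 with S12, S22, S32, S42, S52.
2. In Section 7.2, assign every fourth-character code of S22, S32 and S72 that is in use and not yet listed to vertebral, hip, or non-hip, non-vertebral, and align the non-vertebral list. Where the code does not fix the site, let the medical record decide. For register-traced events without record review, state the assignment in advance.
3. In Section 7.4, correct the femur shaft label so that it agrees with Section 7.2 on S72.2, and report S72.2 separately from S72.3-S72.4 in the 10-year safety tracing.

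The cost is wording in the protocol or the analysis plan. It needs no extra data and no change to the sample size.

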7.2. Secondary outcomes

The secondary outcomes are as follows:

1. Time to first non-vertebral fracture (ICD-10-SE: S22.2, S22.3, S22.4-S22.8, S32.1-S32.5, S42, S52, S72, S82)
2. Time to first new non-hip, non-vertebral fracture (ICD-10-SE: S22.2-S22.8, S32.1-S32.5, S42, S52, S72.3-S72.4, S82)
3. Time to first hip fracture (S72.0-S72.2)
4. Time to first new forearm fracture (S52)
5. Time to first clinical vertebral fracture (S12, S22.0, S22.1, S32.0, M48.5, M49.5, M80.0A, M80.0J, and M80.0K)
6. Time to death

Study Name: The Fragility Fracture Trial
Version No: 2
Date: 2020-10-04
EudraCT No: 2019-004766-17

7. Time to first new cardiovascular event (stroke or myocardial infarction) (ICD-10-SE: I21, I60-I64)
8. Time to first new cancer diagnosis (ICD-7-SE: 140-209)
9. Occurrence of fall from standing height or less (ICD-10-SE: W00, W01, W03, W04, W18) not resulting in fracture between baseline and 48 months

Hip fractures are included among non-vertebral fractures and forearm fractures are included among non-hip, non-vertebral fractures. However, hip fractures and forearm fractures will also be assessed separately because these are common and classic types of osteoporotic fractures. Fractures, myocardial infarction, stroke, and cancer events will be identified through self-report and verified by investigators through review of medical records. Participants will also have the possibility of reporting these outcomes to their study center between the scheduled study contacts. Participants who withdraw will be asked if they wish to answer questions about these outcomes before they formally withdraw.

In the 10-year follow-up, myocardial infarction and stroke will be traced using the above-mentioned ICD-10-SE codes in the National Patient Register, SWEDEHEART, and the Swedish Stroke Register. SWEDEHEART is a register that covers most patients in Sweden who are hospitalized for acute coronary syndrome, coronary interventions, or valvular interventions.⁴⁵ The Stroke Register is a register of Swedish stroke patients, although it does not have complete coverage of the population.⁴⁶ At the 10-year follow-up, cancer events will be identified through the Swedish Cancer Register, which records all new cases of cancer in Sweden since 1958.⁴⁷ Deaths will be identified through the Swedish Cause of Death Register and by reports from family members to study centers.⁴⁸

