3.2. Secondary objectives

The secondary objectives are to investigate whether zoledronic acid, as compared with placebo:

1. has a different effect on new clinical fractures in men and women
2. reduces the risk of cancer
3. reduces the risk of cardiovascular disease (stroke or myocardial infarction)

Study Name: The Fragility Fracture Trial
Version No: 2
Date: 2020-10-04
EudraCT No: 2019-004766-17

4. reduces the risk of death
5. reduces the risk of falling

Although it is conventional to designate subgroup analyses as exploratory, the subgroup analysis by sex was designated as a secondary objective because no clinical trial has shown that bone-protective therapy significantly reduces clinical fractures in men.⁸ This fact may explain part of the low rates of osteoporosis treatment in men.^{16,27} Cancer was selected as a secondary outcome to confirm the results of a recent phase IV trial, which showed a significant reduction in cancer (a pre-specified safety outcome) in osteopenic women treated with zoledronic acid.²¹ Cardiovascular disease was selected because both clinical trial data and observational data have suggested that bisphosphonates protect against stroke and myocardial infarction.^{21,28-30} Death was selected to confirm the results of a phase III trial that demonstrated significantly reduced mortality in hip fracture patients treated with zoledronic acid.²⁰ Falling was selected as an outcome to confirm the results of two trials, one of denosumab and one of zoledronic acid, which showed significant reductions in falls.^{20,31}

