The occurrence of falls will be analyzed as the number and percent of participants reporting at least one fall. Falls will not be analyzed as a time-to-event outcome because participants may not remember exactly when they fell. The zoledronic acid and placebo groups will be compared using relative risks, with 95% confidence intervals estimated based on the normal approximation. Participants with incomplete follow-up and who did not report a fall during follow-up will be assumed not to have fallen.

Change-from-baseline outcomes will be analyzed using analysis of covariance. The response variable will be post-intervention value and the explanatory variables will be baseline value and treatment group. For the EQ-5D-5L exploratory outcomes, which will be measured every 12 months of follow-up, an analysis of covariance will be run with each follow-up value as the post-intervention value. To prevent the problem of multiple testing, the stepwise approach to testing described in Section 13.8 will be used. The assumptions of linearity, constant variance, and normality will be checked using residual plots and normal quantile-quantile plots. Clear violations of these assumptions will be dealt with by transformations of the response variable or its baseline value. Clear violations of the assumption of constant variance may instead be dealt with using the method of weighted least squares. Outliers will not be removed. Participants with missing follow-up data on change-from-baseline variables will be excluded.

The hypothesis tests of efficacy will not be adjusted for multiple testing to avoid a large reduction in the power of the trial.

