13.10. Sample size and power calculations

The trial will enroll 2900 patients, of whom 227 will need to sustain a clinical fracture during follow-up for the study to achieve 90% power to detect a 35% reduction in clinical fractures with the log-rank test (2-sided significance level of 5%). This calculation assumes a 4-year fracture risk of 10% in the placebo group and an overall dropout rate of 5% (due to withdrawal or loss to follow-up, i.e., deaths excluded). The details of the calculation can be found in Appendix 1. Appendix 2 provides a table of required sample sizes under varying assumptions. As shown, the required sample size is sensitive to changes in the assumed hazard ratio and the assumed fracture risk in the placebo group, but it is relatively insensitive to changes in the dropout rate.

To put the assumptions of the sample-size calculation in perspective, we note that 3 of 4 previous large trials of zoledronic acid had 90% power,^{19,20,22} whereas the fourth had 80% power.²¹ Incomplete follow-up (deaths excluded) was observed in 4% of women with osteopenia (6-year follow-up),²¹ 8% of men with osteoporosis (1-year follow-up),²² 13% of women with osteoporosis (3-year follow-up),¹⁹ and 17% of hip fracture patients (1.9-year

Study Name: The Fragility Fracture Trial
Version No: 2
Date: 2020-10-04
EudraCT No: 2019-004766-17

median follow-up).²⁰ Three of the trials that were powered to demonstrate effects on clinical fractures, and these showed effects of 27%,²¹ 33%,¹⁹ and 35%.²⁰

The assumed 4-year fracture risk of 10% was derived from data about the Swedish population that we have previously collected from the Swedish National Patient Register. We selected adults in Sweden who were aged 65 to 85 years and who suffered an initial fracture of the arm or lower leg in 2006 (ICD-10-SE codes: S42, S52, or S82). There were 10,361 such individuals who were not prescribed bone-protective treatment over the next 4 years. Their mean age was 74.9 years and 73% were women. Over the 4 years, 10.0% (n=1028) suffered a new fracture at a different skeletal site. We expect the restriction of the analysis to fractures of a different skeletal site to lead to an underestimation of the incidence of new fractures, but the restriction is necessary to avoid counting the same fracture twice. The distribution of fractures by skeletal site was as follows:

1. 457 fractures of the hip
2. 148 fractures of the upper arm
3. 125 fractures of the lower leg and foot joint

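### The falls outcome leaves out falls that cause a fracture, so it does not match objective 5 and is biased toward placebo in expectation if the drug prevents fractures

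*Protocol*

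**What the plan says.** Section 3.2 lists as secondary objective 5 whether zoledronic acid "reduces the risk of falling", with no restriction on the kind of fall. It adds that "Falling was selected as an outcome to confirm the results of two trials", both of which had shown fewer falls.

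Section 7.2 defines the matching outcome, number 9, as "Occurrence of fall from standing height or less (ICD-10-SE: W00, W01, W03, W04, W18) not resulting in fracture between baseline and 48 months". The version 2 change summary also calls it a fall without fracture, so the restriction is deliberate.

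Section 13.6 states: "The occurrence of falls will be analyzed as the number and percent of participants reporting at least one fall". It continues: "The zoledronic acid and placebo groups will be compared using relative risks, with 95% confidence intervals estimated based on the normal approximation". For those who leave early: "Participants with incomplete follow-up and who did not report a fall during follow-up will be assumed not to have fallen". None of the six sensitivity analyses in Section 13.8 adds fracture falls back.

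The fracture effect that the trial is built on is in Section 13.10 and Appendix 1: a 4-year risk of 10% on placebo and a hazard ratio of 0.65.

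**The concern.** The outcome selects falls by their consequence, and that consequence is the target of treatment. Take one fall that would break a bone on placebo but not on zoledronic acid. It is dropped from the placebo count and kept in the zoledronic acid count, although the participant fell either way. If falling is unaffected and the primary hypothesis is true, the two arms are therefore not expected to show equal proportions. The direction follows from the definition and needs no assumption about fall rates; only the size does.

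At stake is the answer to a named secondary objective. A true reduction in falling would be diluted, and no effect could look like a slight increase. Section 3.3 includes muscle strength as a possible mechanism for a benefit on falls, so a distorted falls result would also cloud that reading. Apart from bias, an outcome that omits the falls with the worst consequences does not measure the risk of falling.

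**Working it through.** **The plan's own figures.** Section 13.10 aims to "achieve 90% power to detect a 35% reduction in clinical fractures with the log-rank test (2-sided significance level of 5"%). Appendix 1 reproduces:

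- Events: 4(1.960 + 1.282)² / ln(0.65)² = 226.5, rounded up to 227.
- Risk on zoledronic acid: 1 − 0.90^0.65 = 0.06619.
- Participants: 227 / ((0.10 + 0.06619)/2) = 2732; 2732/0.95 = 2876, rounded to 2900, or 1450 per arm at 1:1.

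The fracture risks differ by 10.00 − 6.62 = 3.38 percentage points. The false excess in the falls outcome cannot exceed this when falling is unaffected.

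**Inputs that the protocol does not give (assumed).** These are the proportion who ever have a qualifying fall, the pattern of repeat falls, and the share s of fractures caused by qualifying falls. I use negative binomial counts with dispersion 1, the same mean μ in both arms (no effect on falling), and s = 0.9 or 0.7.

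**Formulas.**

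- Ever falls: μ/(1 + μ).
- Per-fall fracture probability q, solved from μq/(1 + μq) = s × fracture risk.
- At least one fall without fracture: μ(1 − q)/(1 + μ(1 − q)).

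**One case in full (μ = 0.5, s = 0.9).** Ever falls = 0.5/1.5 = 33%.

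- Placebo: s × risk = 0.0900, so μq = 0.0900/0.9100 = 0.0989 and q = 0.198. Outcome 9 proportion = 0.4011/1.4011 = 28.6%.
- Zoledronic acid: s × risk = 0.0596, so μq = 0.0596/0.9404 = 0.0633 and q = 0.127. Outcome 9 proportion = 0.4367/1.4367 = 30.4%.
- Relative risk = 1.062. The standard error of its logarithm at 1450 per arm is 0.057, so z shifts by ln(1.062)/0.057 = 1.0.

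**All cases, no effect on falling.**

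| μ | Ever falls | RR, s = 0.9 | z shift | RR, s = 0.7 | z shift |
|---|---|---|---|---|---|
| 0.3 | 23% | 1.143 | 1.7 | 1.095 | 1.2 |
| 0.5 | 33% | 1.062 | 1.0 | 1.043 | 0.8 |
| 0.8 | 44% | 1.029 | 0.7 | 1.021 | 0.5 |
| 2.0 | 67% | 1.006 | 0.2 | 1.005 | 0.2 |

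With s = 0.9, the chance of a significant false increase is about 39%, 18%, 10% and 4% in the four rows, against a nominal 2.5% in that direction.

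**Dilution of a true benefit.** With all fractures attributed to qualifying falls and a true all-falls relative risk of 0.95, the expected relative risk on outcome 9 is 1.02–1.05 if 30% of placebo participants fall and 0.97–0.985 if 50% do (negative binomial to Poisson counts).

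**After the change.** If every qualifying fall counts and all are reported equally well, the expected relative risk under no effect is 1.00 at any fall rate. If all fracture falls but only 70% of the others are reported (an assumption), it is 0.96, 0.98, 0.99 and 0.997 in the four rows with s = 0.9.

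**The case against.** The strongest reply is that the analysis is binary. A participant with a fracture fall and any other qualifying fall still counts; only those whose every qualifying fall broke a bone are lost. Where falls are common and repeated, the bias all but disappears. This stands, and it limits the size.

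The larger figures also rest on demanding inputs. A relative risk of 1.14 needs a third of placebo falls to cause a fracture (q = 0.33). A 90% share may be generous, because only five W-codes qualify, while the primary outcome includes high-energy and vertebral fractures. This also stands, and is why the range goes down to 70%.

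A reader might infer that the trial will show more falls on zoledronic acid, or that the result must favour placebo. The documents do not support that. The bias is in expectation, its size hangs on an unstated fall rate, and in no row of the table does the shift alone reach 1.96.

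It can also be said that the restriction is openly labelled and that fractures are reported separately. Both are true, but separate reporting does not yield the proportion who fell, which objective 5 asks about. If the unqualified wording of Section 13.6, "number and percent of participants reporting at least one fall", was meant to include fracture falls, it conflicts with Section 7.2 and the two need reconciling.

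Finally, the remedy is not free of bias: fractures reach medical attention and registers, while other falls depend on recall at six-monthly contacts. That residual bias favours zoledronic acid and is smaller than the one removed.

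**Conclusion.** The point holds as a mismatch between objective and outcome, with a bias toward placebo in expectation if the drug prevents fractures and does not affect falling. Nothing in Sections 13.6 or 13.8 corrects it. Under the stated model the size runs from negligible (relative risk about 1.005 if 67% ever fall) to about 1.10–1.14 (if 23% do). It rests on the protocol's fracture risks of 10% and 6.62%, and on assumed fall rates, dispersion and a 70–90% share.

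This should be fixed, but it is not critical. It concerns the last of nine secondary outcomes and leaves the primary analysis and the sample size untouched.

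**What to change.** In Sections 7.2 and 13.6, define the falls outcome as at least one fall from standing height or less (the same W-codes) between baseline and 48 months, whether or not it resulted in a fracture. Record the W-code for each incident fracture: Section 7.1 defines incident fractures by S and M codes regardless of energy and does not explicitly ask for the mechanism. Report falls without fracture beside the new outcome as a descriptive component, so that readers can see how much of any difference comes from fracture falls and from uneven reporting.

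The cost is a short wording change in two sections and one extra item per incident fracture. Table 1 already collects falls and fractures at the same contacts, so no new contact is needed. The downsides are some overlap with the fracture outcomes and the smaller residual bias toward zoledronic acid if fracture falls are reported more completely than other falls.
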